### 7.2 Statistical methods for the analysis of study data

#### 7.2.1 Correlating microbiome parameters with treatment outcome

Spearman's correlation coefficient will be used to identify statistically significant associations between (continuous variables) Shannon index at baseline and change in DAS28-CRP from baseline to 3 months post-MTX. In addition, Shannon index and other microbiome characteristics such as taxa and gene abundance will be analysed for covariation with other clinical metadata (CRP, anti-CCP, RF), also using Spearman's correlation coefficient. The predictive capability of the microbiome for MTX response will be assessed by generation of a cross-validated predictive model, using a machine-learning R statistical package such as *randomForest*.

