### 3 Hypothesis

A single microbiome parameter ( $\alpha$ -diversity, microbial diversity measured by Shannon index) in treatment-naïve early RA patients positively correlates with MTX response at 3 months (measured by change in DAS28- CRP) and can be used to predict treatment response in these patients.

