#### 4.1 Primary aim

To determine alterations in gut bacteria and viruses of early RA patients and if specific changes are associated with the outcome of MTX treatment, by estimating the correlation between microbial diversity ( $\alpha$ -diversity measured by Shannon index) and response to MTX measured by change in DAS28-CRP.

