#### 4.2 Secondary aims

1. To explore more broadly the correlations between baseline gut microbiome parameters; such as compositional and functional profiles, and MTX outcome or disease severity measured by DAS28-CRP, Simplified Disease Activity Index (SDAI), CRP, ESR or autoantibody titer.
2. To explore longitudinal alterations to the composition of gut bacteria and viruses in early RA patients throughout 6 months of MTX treatment.
3. To explore if environmental factors such as diet and lifestyle can be used to explain response-associated alterations in bacterial and/or viral populations in early RA patients.
4. To determine if RA patients generate autoimmune responses to their own intestinal microbes (indicative of increased intestinal permeability) and if this changes with treatment, by testing the humoral (antibody) and cellular (peripheral blood mononuclear cell [PBMC]) reactivity against commensal microbes.

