#### 5.5.2.3 Collection of 7-day food diary, baseline health and lifestyle questionnaire and clinical data

The participant's completed 7-day food diary will be collected, and any member of the Study Team will go through a baseline health and lifestyle questionnaire (Appendix 9) with the participant at this stage. No further 7-day food diaries will be provided to the participant for the purpose of this study. A methotrexate treatment record will be provided to the participant (Appendix 23) where they will record the dates and dosages of methotrexate taken. Participants will need to keep this document until they have completed the study, so it will be retrieved at the final study visit (6 month routine treatment review).

After the appointment, a member of the study team with appropriate access to NNUH hospital systems will obtain clinical data including DAS28-CRP (recorded by the clinician) using the Case Report Form (Appendix 11).

[figure not shown]

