### 5.9.2.2 Shotgun metagenomic sequencing

Total microbial DNA will be extracted from stool samples, quantified and sent to Novogene (Hong Kong) for shotgun metagenomic sequencing on the Illumina platform (insert size, 300bp; paired-end read length, 150bp; depth, 10GB data per sample). The resulting sequencing data received from Novogene will be used to identify the  $\alpha$ -diversity (Shannon Index) and bacterial composition and functional profiles in the stool samples. The raw sequences will also be used to identify viral sequences, using a pipeline currently being developed at QIB. Correlations will be drawn between  $\alpha$ -diversity (Shannon Index) and change in DAS28-CRP to answer the primary research aim. Various statistical analyses (see Statistical Methods) will be carried out to determine the diversity (e.g. Shannon index, Bray-Curtis dissimilarity) and differential abundance of microbial genera between responders and non-responders to MTX; which will inform on the reliability of microbiome parameters as predictors of MTX response. This analysis will be carried out by [name] with the support of QIB Bioinformaticians.

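### The primary Spearman test is valid for the marginal correlation, but no stated analysis adjusts for baseline DAS28-CRP, so the plan cannot say whether Shannon index adds to starting severity as a predictor

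*Protocol*

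**What the plan says.** Section 7.2.1 names one test of the primary hypothesis, Spearman's correlation between "Shannon index at baseline and change in DAS28-CRP from baseline to 3 months post-MTX". It names no covariate. This matches section 4.1, where the aim is to estimate the correlation between diversity "and response to MTX measured by change in DAS28-CRP". Section 3 goes on to say that the index "can be used to predict treatment response in these patients". Section 5.9.2.2 plans comparisons of responders with non-responders, "which will inform on the reliability of microbiome parameters as predictors of MTX response".

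The other analyses stated are:

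- **Section 7.2.1, clinical variables.** Shannon index and other microbiome features "will be analysed for covariation with other clinical metadata (CRP, anti-CCP, RF"). DAS28-CRP is not in that list, although secondary aim 1 in section 4.2 covers "correlations between baseline gut microbiome parameters; such as compositional and functional profiles, and MTX outcome or disease severity measured by DAS28-CRP" and further measures.
- **Section 7.2.1, prediction.** "The predictive capability of the microbiome for MTX response will be assessed by generation of a cross-validated predictive model". Its inputs are not named.
- **Section 7.2.2.** A regression of longitudinal change in the microbiome.
- **Section 7.2.3.** Multivariable models for diet and lifestyle factors.

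None of these names baseline DAS28-CRP as a covariate, stratum or reference predictor. The score is available: section 5.5.2.3 has the study team "obtain clinical data including DAS28-CRP (recorded by the clinician) using the Case Report Form (Appendix 11") at the pre-treatment visit, and Figure 4 shows the same.

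**The concern.** Change in DAS28-CRP contains the baseline score, and starting severity usually carries information about how far the score falls. Anyone asking whether Shannon index is useful as a predictor will ask whether it says more than the DAS28-CRP already in the notes. Secondary aim 1 itself treats a link between the microbiome and severity as an open question.

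Two things are at stake. First, a significant unadjusted result would leave open whether diversity or starting severity lies behind it. Second, when Shannon index is unrelated to baseline, leaving baseline-related variation in the change score costs power. An adjusted model chosen after the data of 30 patients have been seen would be post hoc, so it should be written down beforehand.

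**Working it through.** **The plan's own figure.** Section 7.1 gives 82.5% power for r = 0.5 with 30 completers at size 0.05. The formula of the *pwr* package is power = Φ{(z_r − z_c)√(n−3)} plus a negligible opposite tail. Here z_r = atanh(r) + r/[2(n−1)], and z_c = atanh of the critical r on n−2 degrees of freedom. With n = 30, r = 0.5 and two-sided 5%, this gives 82.5%, so the figure is reproduced. It is the Pearson figure. Simulated Spearman power at a true r of 0.5 under normality is about 77%.

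**Assumed inputs.** The documents give neither the correlation of Shannon index with baseline DAS28-CRP (the link, a) nor that of baseline with improvement (b). Improvement is baseline minus 3-month score. Assume a baseline SD of 1.1, a 3-month SD of 1.2 and a correlation between them of 0.4. Then:

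- SD of change = √(1.1² + 1.2² − 2×0.4×1.1×1.2) = √1.594 = 1.26, inside the 1 to 1.3 of section 7.1.
- b = (1.1² − 0.4×1.1×1.2)/(1.1×1.26) = 0.682/1.389 = 0.49.

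**Power at the design effect.** Hold the marginal correlation at 0.5. The partial correlation given baseline is (0.5 − ab)/√[(1−a²)(1−b²)]. Powers are simulated (40,000 trials of n = 30, multivariate normal). The adjusted test is that of the Shannon coefficient in a linear regression on Shannon index and baseline.

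| Link a | Partial r | Spearman | Adjusted regression |
|---|---|---|---|
| −0.3 | 0.78 | 77% | over 99% |
| 0 | 0.57 | 77% | 92% |
| +0.2 | 0.47 | 77% | about 75% |
| +0.3 | 0.42 | 77% | about 65% |

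At a = 0, part of the 77% to 92% gap is rank against linear testing. Like for like, it is 77% against 87% (Spearman, partial Spearman) or 83% against 92% (Pearson, regression).

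**No Shannon effect given baseline.** The marginal correlation is then a×b. At a = +0.3 this is 0.3×0.49 = 0.15, and Spearman rejects in the hypothesised direction in about 11% of trials. At +0.2 it is 0.10 and 7%. At zero it is nominal (about 2.5% per side), and at −0.3 it is 0.4%. The adjusted test stays near 2.5% per side throughout.

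**Cost in degrees of freedom.** One covariate at a partial r of 0.5 corresponds to n = 29 in the same formula: 81.1% instead of 82.5%.

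**Limit of the adjusted model.** Suppose Shannon index tracks stable severity, baseline DAS28-CRP measures that severity with error, and improvement does not depend on it. At a link of −0.3 the adjusted test then rejects in the hypothesised direction in about 5% of trials (reliability 0.8) to 19% (reliability 0.5). Spearman stays at 2.4% to 2.6% per side.

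**The case against.** The strongest reply is that the protocol does not set out to show prediction beyond severity. Sections 3 and 4.1 ask for a correlation and for use as a predictor, and a marginal predictor can still predict. This stands. A reader might infer that the primary test is invalid, or that the plan fails a claim of its own. The documents support neither, because Spearman estimates what the aim asks for.

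A reader might also infer that unadjusted power collapses if sicker patients have lower diversity. Holding the partial correlation at 0.574 with a link of −0.3 does give Spearman about 39%. But the marginal correlation is then only 0.33, below the 0.5 for which section 7.1 plans. At the design effect Spearman stays near 77%. Which test has more power depends on the sign of a link that the documents do not give.

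The severity-only rejections need a positive link, and nothing in the documents points to one. Section 2.2 reports reduced diversity in RA, which is not evidence on severity within RA.

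It can also be said that supportive analyses belong in an SAP, that the predictive model might include baseline DAS28-CRP, and that the clinical list in section 7.2.1 is merely abbreviated, since it omits SDAI and ESR too. The last point stands: the omission calls only for alignment with secondary aim 1. The other two do not close the gap. The protocol has itself fixed the primary analysis, and a model with unnamed inputs gives no stated comparison with baseline DAS28-CRP.

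**Conclusion.** The point holds as a cheap improvement and not as an error in the primary test. As written, the plan can show whether baseline Shannon index correlates with change in DAS28-CRP. It cannot say whether the index adds to starting severity, which bears on the predictive use in sections 3 and 5.9.2.2.

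The size is unknown, because both correlations that drive it are assumed. On those assumptions adjustment gains about 10 percentage points of power like for like if Shannon index is unrelated to baseline, more if the link is negative, and loses power if it is clearly positive. The roughly 11% of severity-only rejections at a link of +0.3 might be read as an inflated type I error. It is not: the marginal correlation there is truly 0.15, so the marginal null is false. The figure misleads only if a significant result is taken to mean prediction beyond severity.

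**What to change.** In section 7.2.1:

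1. Keep the Spearman correlation as the primary test.
2. Prespecify one supportive linear regression of 3-month DAS28-CRP on baseline Shannon index and baseline DAS28-CRP, reporting the Shannon coefficient with its 95% confidence interval.
3. Add DAS28-CRP to the listed clinical variables, to match secondary aim 1, and report its baseline correlation with Shannon index with a confidence interval. At n = 30 this will be imprecise: an observed −0.3 has an interval of about −0.60 to 0.08.
4. Make any statement about prediction beyond baseline severity only from the adjusted estimate and its interval, with the caveat that measurement error in baseline DAS28-CRP can bias it.

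Do not require significance in both tests, and do not add a rule triggered by the two analyses differing. Such a rule would be undefined, and chance differences are likely at this sample size.

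The cost is two or three sentences and no new data. The supportive model loses one degree of freedom, has less power than Spearman if Shannon index rises with severity, and may be biased by error in the baseline score. For these reasons it should stay supportive and not replace the primary test.

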#### 7.2.2 Identifying microbiome alterations induced by methotrexate

Longitudinal changes to the microbiome during MTX treatment will be studied using a regression model. Alterations to the microbiome throughout methotrexate treatment will also be visualized using principle coordinates analysis (PCoA) and  $\beta$ -diversity (Bray-Curtis dissimilarity; between-sample diversity). This analysis will be done using an R package such as *vegan*.

#### 7.2.3 Other statistical analyses

Multivariable models will be developed to explore whether diet and lifestyle factors can help account for any alterations seen in the microbiome associated with treatment response. Blood work will mainly consist of ELISA, for which parametric tests will be used to determine the signal strength of fluorescence from each sample, corresponding to the titer of antibodies against enteric microbes. All analyses will be conducted in R, GraphPad Prism or similar statistical programs.

## 8 Resource requirements

### 8.1 Staffing requirements

Processing and analysis of samples and data will be carried out primarily by [name], a PhD Student at UEA for whom a maintenance stipend is provided by a Faculty of Medicine and Health Science Studentship, and for which this study will form the main part of a PhD. In addition, [name] or another NOAR Research Nurse may be required to take blood samples, assist with consenting participants and collecting stool samples. Novogene (Hong Kong) services will be used for shotgun metagenomic sequencing.

### 8.2 Material requirements

A successful funding application to the local Norfolk charity Action Arthritis (Registered Charity Number 292569) has provided £18,629.02 for lab consumables and study materials (Appendix 16). The 7-day food diaries are already available for use at the BCREB. A short general health questionnaire has been generated by [name] for use in a larger project (the MOTION study, IRAS no. 241617, ethical application still in progress) to encompass factors affecting the intestinal microbiome, such as exercise, medications and lifestyle.

## 9 Confidentiality

All members of the Study Team will be fully compliant with the requirements of the EU General Data Protection Regulation (GDPR) 2016/679 and the UK Data Protection Act (DPA) 2018 with regards to the collection, storage, processing and disclosure of personal information and will uphold the GDPR and DPA core principles to maintain confidentiality. Personal information will be anonymized in a linked form on receipt, by using a unique identifier consisting of an unrelated sequence of characters and numbers, and stored securely in a locked file cabinet at QIB with keys available only to members of the study team. Linked data will be also only be accessible by the study team and will stored in an encrypted or password-protected database on UEA or QIB computers. The data will be stored for 15 years in case it is required for further research, and the data custodian will be [name].

## 10 Ethical considerations

As this study involves the recruitment and participation of human subjects from the National Health Service (NHS), appropriate Research Ethics Committee (REC) approval will be obtained by applying to the Health Research Authority (HRA) via the Integrated Research Application System (IRAS).

### 10.1 Informed consent

Written informed consent will be obtained from participants entering into the study by an appropriately trained member of the Study Team or Rheumatology Clinician, and members of the Study Team will continuously ensure the participants are happy to continue with the study and provide samples, in accordance with National Institute for Health Research Good Clinical Practice (GCP) guidelines.

### 10.2 Risks associated with study procedures

The risks associated with venipuncture such as discomfort and bruising will be minimized as only an appropriately trained HCA/Phlebotomist at NNUH will carry out this procedure, unless they are unable to do so for any reason in which case an appropriately trained member of the Study Team (e.g. the NOAR Research Nurse) will carry out the procedure.

### 10.3 Reporting of Serious Adverse Events

As this study does not involve any intervention or procedure which will not be part of the participant's routine clinical care, we will not officially record any Serious Adverse Events (SAEs).

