#### 5.5.2.2 Collection of blood sample

The on-duty Healthcare Assistant (HCA) or Phlebotomist at the NNUH; who will be taking approximately 4ml blood as part of the participant's routine clinical care (to test for inflammatory biomarkers), will be asked to obtain an additional 40 mL blood sample during the same procedure to minimize inconvenience to the participant. This additional 40 mL blood sample will be collected solely for the purpose of this study, and in the form of 2 x 10 mL whole blood (20 mL in Vacutainer EDTA tubes) and 2 x 10 mL serum (20 mL in Vacutainer SST tubes).

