### 5.5.3 Third and fourth appointments: Routine Treatment Review

The following two data collection points will coincide with routine treatment review appointments organized as part of the participant's normal care pathway (at approximately 3 and 6 months from the NP appointment or time of commencing MTX/post-MTX).

The 3-month appointment will reflect the NP appointment in that another 40 mL blood sample will be taken for the purpose of this study by the on-duty HCA/Phlebotomist; as per Section 5.5.2.2, and the participant's stool sample will be collected from them as per Section 5.5.2.1. Clinical data will be recorded by a member of the study team with appropriate access to NNUH hospital systems using the Case Report Form (Appendix 11). Any member of the Study Team will go through another health

and lifestyle questionnaire with the participant, although this will be a shortened partial version of the questionnaire aimed at identifying changes (if any) from the NP appointment (Appendix 10). The participant will be provided with another stool collection kit for the final stool sample to be

**Figure 3:** Flowchart of involvement of participants in the study

brought to their next treatment review (at 6 months post-MTX, approximately 3 months after their 3-month treatment review).

At the 6-month treatment review, the participant's final stool sample will be collected as previously, any member of the Study Team will go through a final follow-up health and lifestyle questionnaire (Appendix 10) with the participant and their methotrexate treatment record (Appendix 23) will be collected. Clinical data will be recorded by a member of the study team with appropriate access to NNUH hospital systems using the Case Report Form (Appendix 11). No further blood samples will be taken for the purpose of this study at this 6-month treatment review. Following this final appointment, no further information will be required from the participant and their involvement with this study will end. Their routine care will continue as normal.

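### Section 10.3 waives recording of SAEs on the ground that nothing goes beyond routine care, but the protocol itself specifies study-only blood and stool sampling, so an SAE related to that sampling would not be officially recorded

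*Protocol*

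**What the plan says.** Protocol Section 10.3 says that "we will not officially record any Serious Adverse Events (SAEs". Its only ground is that "this study does not involve any intervention or procedure which will not be part of the participant's routine clinical care". The waiver covers all SAEs, with no exception for events related to study sampling.

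Other sections describe sampling done for the study:

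- **Baseline blood.** In Section 5.5.2.2, hospital staff "who will be taking approximately 4ml blood as part of the participant's routine clinical care" and "will be asked to obtain an additional 40 mL blood sample during the same procedure to minimize inconvenience to the participant". The section adds: "This additional 40 mL blood sample will be collected solely for the purpose of this study".
- **Blood at 3 months.** Section 5.5.3 says "another 40 mL blood sample will be taken for the purpose of this study by the on-duty HCA/Phlebotomist". At 6 months there is none: "No further blood samples will be taken for the purpose of this study at this 6-month treatment review".
- **Stool.** Sections 5.5.1.2, 5.5.2.1 and 5.9.2.1 have participants collect stool with a kit supplied by the study, for three time points. The study team sometimes fetches the sample from the participant's home. The protocol nowhere presents this as routine care.
- **Risk.** Section 10.2 is headed as dealing with the risks of study procedures. It names discomfort and bruising from venepuncture and provides that, if hospital staff cannot take the blood, "an appropriately trained member of the Study Team (e.g. the NOAR Research Nurse) will carry out the procedure".

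**The concern.** A waiver of SAE recording can be reasonable in an observational cohort where participants undergo nothing beyond their usual care. Section 10.3 relies on exactly that condition, and this study does not meet it. Someone who read Section 10.3 alone, for instance on an ethics committee, would be told that no study procedure exists, while the preceding section discusses the risks of study procedures.

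Participant protection is at stake, not the analysis. If a serious event followed a study blood draw, the protocol would direct the team not to record it officially, and no other section gives a route to the sponsor or the ethics committee.

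**Working it through.** **Inputs**

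- Study blood per visit: 2 x 10 mL EDTA tubes and 2 x 10 mL serum tubes (Section 5.5.2.2).
- Visits with a study draw: two, baseline and 3 months (Sections 5.5.2.2 and 5.5.3; Figure 4).
- Routine blood at the baseline draw: about 4 mL (Section 5.5.2.2).
- Participants: 30 to complete, 35 as the recruitment target (Sections 5.3 and 7.1).

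**Step 1: reproduce the protocol's own figure.** Per visit, 2 x 10 + 2 x 10 = 40 mL. Over two visits, 2 x 40 = 80 mL. This agrees with the total in Section 5.9.1.1, so the sections on blood volume are consistent with one another. Section 10.3 is the outlier.

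**Step 2: how much of the draw is for the study.** At the baseline visit, 40 / (40 + 4) = 40/44, about 91% of the blood taken. This describes what the draw is for. It does not measure risk.

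**Step 3: number of study draws under the waiver.** 30 completers x 2 = 60 draws. If all 35 recruits gave both samples, 35 x 2 = 70 draws.

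**Step 4: set the premise against the text.**

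| Premise of Section 10.3 | What the protocol provides |
|---|---|
| No procedure outside routine care | 40 mL of blood for study purposes only, twice (5.5.2.2, 5.5.3, 5.9.1.1) |
| No procedure outside routine care | Stool collection with study kits at three time points, with home pick-up where needed (5.5.1.2, 5.5.2.1, 5.9.2.1) |
| No procedure outside routine care | A section on the risks of study procedures, with study staff as fallback for the draw (10.2) |

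**Step 5: look for another route.** The Case Report Form items listed in Section 5.7 are disease activity, inflammatory markers, autoantibodies, height and weight, and stool score. No adverse-event item is named. The form itself (Appendix 11) is not shown, so it is unknown whether it has such a field. No section of the body text describes recording or reporting of a related SAE.

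**The case against.** The strongest reply is that the needle is routine. Section 5.5.2.2 has the extra blood taken during the same venepuncture as the clinical sample, so in the planned case participants have more tubes filled but no extra needle insertion. On that reading, Section 10.3 means only that the venepuncture would happen anyway. In addition, the harms named in Section 10.2 are not in themselves serious, study staff draw blood only as a fallback, and the study is a small observational cohort with no safety aim.

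Much of this stands, and it makes the added risk small. It does not rescue the premise. Blood taken only for research is not part of routine care merely because it comes through the same needle, and the reply does not cover stool collection at all.

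A reader might also infer more than the documents support:

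- *That harm of any kind would go unrecorded.* Section 10.3 concerns serious events and official recording only.
- *That no event could be detected.* Blood is drawn at hospital appointments, study staff with access to hospital systems complete the Case Report Form, and questionnaires at 3 and 6 months ask about changes. None of this is an SAE process, but an event could still come to notice.
- *That a study volume ten times the routine one (40 mL against about 4 mL) means ten times the risk.* Nothing in the protocol links volume to serious harm.
- *That the study could not later claim its procedures were safe.* The protocol plans no such claim.

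**Conclusion.** The point holds as an internal contradiction with a limited practical consequence. The sole reason given for not recording SAEs is incorrect on the protocol's own text. As a result, a serious event related to study sampling would not be officially recorded and has no described reporting route.

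The exposure is 80 mL of study-only blood per participant over two visits, 60 to 70 draws in all if every planned sample is taken, plus three stool collections per participant. The protocol gives no event rate, so no expected count can be calculated. A serious event is unlikely given the shared venepuncture. The primary correlation, its power and the sample size are unaffected.

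The conclusion assumes that no appendix outside the document at hand sets up a route for related SAEs. If one does, the sentence in Section 10.3 still contradicts the sampling sections and still needs correcting. The change should be made because it concerns participant protection and costs little.

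**What to change.** Reconcile Section 10.3 with Sections 5.5.1.2, 5.5.2.1, 5.5.2.2, 5.5.3, 5.9.1.1, 5.9.2.1 and 10.2:

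1. Delete the claim that no procedure lies outside routine care.
2. State that the study-specific procedures are the additional blood, normally taken at a routine venepuncture, and the stool collection.
3. State that SAEs judged related to these procedures will be recorded and reported to the sponsor and the ethics committee, and that unrelated SAEs need not be.

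Correcting the premise alone would remove the contradiction but leave related events without a route, so the third step is worth including. Restricting it to related events keeps the burden in proportion to an observational study.

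The cost is one paragraph and, if the Case Report Form lacks one, one field. Sampling, visits and analyses do not change.
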